## CLINICAL TRIAL PROTOCOL SYNOPSIS

Name of company: Boehringer Ingelheim		Tabulated Trial Protocol			
Name of finished product: Not Applicable					
Name of active ingredient: BI 836826					
Protocol date: 25 Feb 2011	Trial number: 1270.2		Revision date: 13 Apr 2016		
Title of trial: A Phase I, Open-Label, Dose-Escalation Trial with BI 836826 in Patients with Relapsed or Refractory non-Hodgkin Lymphoma of B cell Origin					
Co-ordinating Investigator:					
Trial sites:	Multi-centre trial				
Clinical phase:	Phase I				
Objectives:	To investigate the maximum tolerated dose (MTD), safety and tolerability, and efficacy of BI 836826 monotherapy in patients with relapsed or refractory non-Hodgkin lymphoma				
Methodology:	Open-label dose-escalation				
No. of patients:	Approximately 66				
total entered:	Approximately 53				
each treatment:	1 to 6 patients at each dose level, up to 4 patients treated at the 100 mg dose in expansion cohort, additional cohort (up to 12) of Korean patients:3-6 patients at 50 mg, and 3-6 patients at 75 mg				
Diagnosis :	Non-Hodgkin lymphoma of B cell origin				
Main criteria for inclusion:	Relapsed or refractory non-Hodgkin lymphoma of B cell origin not eligible for intensive anti-lymphoma treatment				
Test product:	BI 836826				
dose:	Starting dose will be 1 mg				

Proprietary confidential information.

© 2016 Boehringer Ingelheim International GmbH or one or more of its affiliated companies. All rights reserved.

This document may not - in full or in part - be passed on, reproduced, published or otherwise used without prior written permission.

Name of company: Boehringer Ingelheim		Tabulated Trial Protocol		
Name of finished product: Not Applicable				
Name of active ingredient: BI 836826				
Protocol date: 25 Feb 2011	Trial number: 1270.2		Revision date: 13 Apr 2016	
mode of admin. : BI 836826 administered intravenously as single agent treatment				
Comparator products: Not applicable				
dose:				
mode of admin. :				
Duration of treatment: Patients are eligible for up to 3 courses with a total of 12 administrations of BI 836826. Each course comprises of 4 administrations in weekly intervals followed by treatment free observation/rest. The duration of two first courses is each 7 weeks and the duration of the third course is 12 weeks. The maximum duration of treatment and observation period/rest is 26 weeks before follow-up.				
Criteria for efficacy and pharmacodynamics: Reduction in tumour size, best overall response, progression free survival, failure free survival, plasma concentration time profiles				
Criteria for safety: Maximum tolerated dose, incidence and intensity of adverse events graded according to the common terminology criteria for adverse events (CTCAE, version 4.0), incidence of dose limiting toxicity, laboratory parameters.				
Statistical methods: Descriptive statistics				

## FLOWCHARTS

### Flowchart for Course 1

Trial Periods	Screen	Treatment and observation/rest										EOT	FU
Course *		1											
Week		1		2		3		4		5		6	7
Visit **	Screen	1	2	3	8	9	10	15	17	22	29	36	43
Days	-14 to -1	1	2	3	8	9	10	15	17	22	29	36	43
Informed consent	x												
Demographics	x												
Medical history	x												
Review of in-/exclusion criteria	x	x 1											
Eligibility for trial	x												
12-lead ECG	x												
Height	x												
Weight	x	x	x	x	x	x	x	x	x	x	x	x	
Physical examination, incl. tumour size (lymph nodes, spleen, liver),	x	x								x			x
Vital signs 	x	x	x	x	x	x	x	x	x	x	x	x	x
Dose assignment	x 												
Concomitant therapy	x	x	x	x	x	x	x	x	x	x	x	x	x
General safety laboratory parameters 	x	x	x	x	x	x	x	x	x	x	x	x	x
Administration of BI 836826		x		x			x		x	x			
Screening for Tumour Lysis Syndrome 		x	x		x	x							
Adverse events		x	x	x	x	x	x	x	x	x	x	x	x
Disease/response assessm. (clinical/imaging)	x	x 6							x 				x 
Serum pregnancy test 	x	x							x				
CMV monitoring 	x	x					x		x	x	x	x	x
Lymphocyte typing (B/T/NK cells)		x		x	x		x	x	x	x	x	x	x
Virology screening  (HBV, HCV, HIV, CMV)	x												
CT scan of neck, thorax, abdomen and pelvis	x 												

Proprietary confidential information.

© 2016 Boehringer Ingelheim International GmbH or one or more of its affiliated companies. All rights reserved.

This document may not - in full or in part - be passed on, reproduced, published or otherwise used without prior written permission.

EOT: End of treatment visit, to be performed at withdrawal from further treatment (<12 administrations) or at the latest 8 weeks after the last administration of BI 836826 (12 administrations)

FU: Follow-up visits (starts after EOT) at least every 6 weeks until 6 months after EOT visit, details see [section 6.2.3.2](#)

CMV: Cytomegalovirus

HBV: Hepatitis B virus

HCV: Hepatitis C virus

HIV: Human immunodeficiency virus

\* the planned duration of course 1 is 7 weeks (49 days)

\*\* the visit number follows the course number, i.e. visit 2 course 1 will read C1\_V2 and visit 2 course 2 will read C2\_V2 ...

- 1 Review of eligibility
- 2 For details during and after infusion of BI 836826, refer to [section 5.2.5.1](#)
- 3 After informed consent, and review of in- and exclusion criteria, and before the first administration of the trial drug
- 4 For details refer to [section 5.2.3.1](#)
- 5 Screening for tumour lysis syndrome in between safety laboratory assessments ([section 5.2.3.2](#))
- 6 Disease / response assessment will be based on clinical judgement when recent CT is not available
- 7 For women of childbearing potential only (please refer to sections [3.3.3](#) (exclusion criterion 20) and [5.2.3.1](#))
- 8 Quantitative CMV DNA PCR ([section 5.2.3.3.2](#))
  
- 10 Please refer to [section 5.2.3.3.1](#)
- 11 CT scan may be performed up to 4 weeks prior to first infusion according to the standard of care in this patient population

**Proprietary confidential information.**

**© 2016 Boehringer Ingelheim International GmbH or one or more of its affiliated companies. All rights reserved.**

This document may not - in full or in part - be passed on, reproduced, published or otherwise used without prior written permission.

Flowchart for Course 2

Trial Periods	Treatment and observation/rest										EOT	FU
Course *	2										If clinical benefit and agreement on further treatment for the patient, please continue to Visit 1 Flowchart for Course 3	If the patient has disease progression or withdraws, please continue to EOT visit on Flowchart for Course 3
Week	8		9		10		11		12		13	14
Visit **	1	2	3	8	5	6	7	8	9	10		
Days	1	2	3 +2	8 +4	15	17 +2	22	29 ±2	36 ±5	43 ±2		
Eligibility for course 2	x 											
Vital signs 	x	x	x	x	x	x	x	x	x	x	x	x
Weight	x	x		x		x		x			x	
Physical examination, incl tumour size (lymph nodes, spleen, liver)	x							x			x	
Disease / response assessment (clinical/imaging)	x 							x 			x 	
Serum pregnancy test 	x							x				
Concomitant therapy	x	x	x	x	x	x	x	x	x	x	x	x
General safety laboratory parameters 	x	x	x	x	x	x	x	x	x	x	x	x
Administration of BI 836826	x			x		x		x				
Screening for Tumour Lysis Syndrome 	x	x		x								
Adverse events	x	x	x	x	x	x	x	x	x	x	x	x
CMV monitoring 	x			x		x		x	x	x	x	x
Lymphocyte typing (B/T/NK cells)	x		x	x	x	x	x	x	x	x	x	x
CT scan of neck, thorax, abdomen and pelvis											x	

EOT: End of treatment visit, to be performed at withdrawal from further treatment (<12 administrations) or at the latest 8 weeks after the last administration of BI 836826 (12 administrations)

FU: Follow-up visits (starts after EOT) at least every 6 weeks until 6 months after EOT visit, details see [section 6.2.3.2](#)  
CMV: Cytomegalovirus

\* the planned duration of course 2 is 7 weeks (49 days)

\*\* the visit number follows the course number, i.e. visit 2 course 1 will read C1\_V2 and visit 2 course 2 will read C2\_V2

- 1 Can be performed within 7±2 days prior to this visit
- 2 For details during and after infusion of BI 836826, refer to [section 5.2.5.1](#)
- 3 Disease / response assessment will be based on clinical judgement when recent CT is not available. Radiological assessments will be performed following the local standard of care.
- 4 Assessment can be performed prior to visit 10, if CT scan from visit 9 is available.
- 5 For women of childbearing potential only (please refer to sections [3.3.3](#) (exclusion criterion 20) and [5.2.3.1](#))
- 6 For details refer to [section 5.2.3.1](#)
- 7 Screening for tumour lysis syndrome in between safety laboratory assessments ([section 5.2.3.2](#))
- 8 Quantitative CMV DNA PCR ([section 5.2.3.3.2](#))

Proprietary confidential information.

© 2016 Boehringer Ingelheim International GmbH or one or more of its affiliated companies. All rights reserved.

This document may not - in full or in part - be passed on, reproduced, published or otherwise used without prior written permission.

Flowchart for Course 3, End of Treatment visit and Follow-up

Trial Periods	Treatment and observation/rest									EOT	FU
Course *	3										
Week	15	16	17	18	19	20	21	23	25	see 	
Visit **	1	2	3	4	5	6	7	8	9		
Days	1	8	15	22	29 (+2)	36 (+5)	43 (+5)	57 (±5)	71 (±5)		
Eligibility for course 3	x 										
Vital signs 	x	x	x	x	x	x	x	x	x	x	x
Weight	x	x	x	x	x	x	x	x	x	x	x
Physical examination, incl. tumour size (lymph nodes, spleen, liver),	x			x			x			x	x
Disease / response assessment (clinical/imaging)	x			x 						x	x 
Serum pregnancy test 	x			x						x	
Concomitant therapy	x	x	x	x	x	x	x	x	x	x	x 
General safety laboratory parameters 	x	x	x	x	x	x	x	x	x	x	x
Administration of BI 836826	x	x	x	x							
Screening for Tumour Lysis Syndrome 	x	x									
Adverse events	x	x	x	x	x	x	x	x	x	x	x 
CMV monitoring 	x	x	x	x	x	x	x	x	x	x	x
Lymphocyte typing (B/T/NK cells)	x	x	x	x	x	x	x	x		x	x
CT scan of neck, thorax, abdomen and pelvis									x	x 	
12-lead ECG										x	
Completion of active trial treatment										x	
Status (remission, progression, death)										x	x
Other therapy for lymphoma										x	x

EOT: End of treatment visit, to be performed at withdrawal from further treatment (<12 administrations) or at the latest 8 weeks after the last administration of BI 836826 (12 administrations)

FU: Follow-up visits (starts after EOT) at least every 6 weeks until 6 months after EOT visit, details see [section 6.2.3.2](#)

CMV: Cytomegalovirus

\* the planned duration of course 3 is 12 weeks (84 days)

\*\* the visit number follows the course number, i.e. visit 2 course 1 will read C1\_V2 and visit 2 course 2 will read C2\_V2 ...

1 Can be performed within 7±2 days prior to this visit

2 For details during and after infusion of BI 836826, refer to [section 5.2.5.1](#)

3 Disease / response assessment will be based on clinical judgement when recent CT is not available

4 For women of childbearing potential only (please refer to [sections 3.3.3](#) (exclusion criterion 20) and [5.2.3.1](#))

5 Concomitant therapy during FU only in case indicated for treatment of an AE (section [4.2.1](#))

6 For details refer to section [5.2.3.1](#)

7 Screening for tumour lysis syndrome in between safety laboratory assessments (section [5.2.3.2](#))

8 For AE assessment during FU refer to sections [5.2.1](#) and [6.2.3.2](#)

Proprietary confidential information.

© 2016 Boehringer Ingelheim International GmbH or one or more of its affiliated companies. All rights reserved.

This document may not - in full or in part - be passed on, reproduced, published or otherwise used without prior written permission.

9      Quantitative CMV DNA PCR (section [5.2.3.3.2](#))

11     In case end of treatment occurs before week 26, a CT scan can be performed at the EOT visit if clinically indicated for response assessment (*e.g.* progression)

12     If 12 infusions has been administered the EOT should be performed at the latest in week 26 (day 77±5 of course 3)

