**Proprietary confidential information.**

**© 2016 Boehringer Ingelheim International GmbH or one or more of its affiliated companies. All rights reserved.**

This document may not - in full or in part - be passed on, reproduced, published or otherwise used without prior written permission.

Clinical disease status will be assessed at screening, at the administration of the first and the last of the 4 infusions and 3 weeks after the last infusion of a respective course with physical examination, clinical assessment of the B-NHL, and blood samples. CT scans in this trial will be performed in accordance with published guidelines for response evaluation in lymphoma ([R04-1585](#)) and correspond to the use in clinical practice ([section 5.1.2.2](#)). A CT scan will be done prior to treatment (may be performed up to 8 weeks (preferably 4 weeks) prior to first infusion), after 2 courses of treatment, (*i.e.* at week 13 +/- window), and just before the end of treatment (EOT) visit (*i.e.* week 25 +/- window). If the CT scans are not possible or available, magnetic resonance imaging can be used instead. However the same imaging methods should be used consistently throughout the trial. Bone marrow examination, PET scan and additional CT scans will be performed at the discretion of the investigator. Results of CT scan, optional PET scan or bone marrow examination performed during the conduct of the trial should be reported in the eCRF. After the EOT visit which may occur at the latest at week 26, the patient will enter the follow-up phase. During the follow-up phase, disease status evaluations (physical examination, clinical assessment of lymphoma, and blood samples) should be performed at least every 6 weeks until 6 months after the EOT visit, administration of new anti-lymphoma therapy or death, whatever occurs first. More frequent visits may be indicated, *e.g.* for follow-up of laboratory parameters or adverse events which have not been resolved at the EOT visit.

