## 6.2.2 Treatment periods

The treatment is given in courses with 4 administrations of a weekly infusion followed by observation/rest. Patients can receive up to three courses, *i.e.* 12 administrations. The duration of the first two courses is 7 weeks and for the third course 12 weeks, hence a 3-week or an 8-week observation/rest after the infusions of BI 836826.

### 6.2.2.1 Course 1

In the first course there are 4 visits with treatment and 6 visits for safety assessment. The first two administrations are given as an in-hospital stay for safety, tumour lysis assessment

Between the visits with infusion of BI 836826 safety visits will be performed. After last infusion the safety visits will be weekly. Clinical disease assessment will be performed at the first infusion visit (visit 1) and the last infusion visit (visit 7) as well as the last visit in the course (visit 10).

For details see [flowchart](#) for Course 1.

In case of the split first dose administration patients are required to be hospitalized under close surveillance with access to intensive care for at least 72 hours after the start of the low dose of BI 836826 to allow close monitoring for infusion-related reactions. Please refer the flowchart in [section 10.7](#) for clinical disease, safety

### 6.2.2.2 Course 2

In the second course there are 4 visits with treatment and 6 visits for safety and response assessment. The first administration is given as an in-hospital stay for safety, tumour lysis assessment

Between the visits with infusion of BI 836826 safety visits will be performed. After last infusion the safety visits will be weekly. Clinical disease assessment will be performed at the first infusion visit (visit 1) and the last infusion visit (visit 7). A CT scan of neck, thorax, abdomen and pelvis must be performed at visit 9 to be available for the disease assessment and response evaluation that are planned to be done at the last visit in the course 2 (visit 10).

For details see [flowchart](#) for Course 2.

### 6.2.2.3 Course 3

In the third course there are 4 visits with treatment and 5 visits for safety and response assessment. All infusions can be given as out-patient, if recent previous infusions have been well tolerated. Clinical disease assessment will be performed at the first (visit 1) and at the last infusion (visit 4).

Proprietary confidential information.

© 2016 Boehringer Ingelheim International GmbH or one or more of its affiliated companies. All rights reserved.

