
This document may not - in full or in part - be passed on, reproduced, published or otherwise used without prior written permission.

CT scan of neck, thorax, abdomen and pelvis will be performed at visit 9 (week 25) unless the EOT visit is performed prior to week 26. Disease assessment, response evaluation with CT scan (see appendix [10.1](#)) will be done at the EOT visit (see below section [6.2.3.1](#)). For details see [flowchart](#) for Course 3.

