Patients administered a new additional therapy for NHL recorded in the electronic case report form (eCRF) but not presenting with disease progression before the start of this new NHL therapy will be censored at the date of last response assessment during which the patient was evaluable and did not have the event before the new NHL therapy has started.

Patients not administered another NHL therapy and not presenting with disease progression or death during the trial will be censored at the date of the last response assessment during which the patient was evaluable and did not have the event.

A patient is said to have an evaluable response assessment if a response of CR, CRu, PR, SD or PD has been assigned.

The censoring rules and the applicable dates of outcome for PFS are given in the following table.

Table 5.2.2:1 Derivation rules for progression-free survival

Situation	Outcome (event or censored)	Date of outcome
Baseline and post-baseline disease assessment: disease progression or death without prior additional NHL therapy	Event	Date of first disease progression or death
Baseline and post-baseline disease assessment: disease progression or death and prior additional NHL therapy	Censored	Date of last response assessment before start of new NHL therapy
Baseline and post-baseline disease assessment: No disease progression or death without additional NHL therapy	Censored	Date of last response assessment
Baseline and post-baseline disease assessment: No disease progression or death with additional NHL therapy	Censored	Date of last response assessment before start of new NHL therapy
No baseline or post-baseline disease assessment: without death	Censored	Date of first administration of BI 836826
No baseline or post-baseline disease assessment: death on or before the first planned disease assessment (i.e. at week 4 assessment)	Event	Date of death
No baseline or post-baseline disease assessment: death after first planned disease assessment (i.e. at week 4 assessment)	Censored	Date of first administration of BI 836826

Remark: determination of the response status via disease assessment refers to any disease assessment via imaging or via physical assessment

Progression free survival (PFS) [in days] is therefore the time from first administration of study medication to the earlier date of disease progression or death (minimum date of disease progression or death – date of first administration of study medication + 1).

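### Protocol section 3.2 asks for a disease assessment 21 days after the final infusion of every course, but course 3 schedules no recorded response at visit 7 (day 43), so progression there can be dated late

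*Protocol*

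**What the plan says.** Protocol section 3.2 sets three time points for clinical disease status in a course: the first infusion, the last infusion, and "3 weeks after the last infusion of a respective course with physical examination, clinical assessment of the B-NHL, and blood samples". It makes no exception for course 3.

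Courses 1 and 2 follow this. For course 1, section 6.2.2.1 places the later assessments at "the last infusion visit (visit 7) as well as the last visit in the course (visit 10"); visit 10 is day 43. In course 2 the response evaluation is also at visit 10.

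Course 3 does not. Section 6.2.2.3 states: "Clinical disease assessment will be performed at the first (visit 1) and at the last infusion (visit 4"). After that it gives only the response evaluation at EOT, supported by imaging: "CT scan of neck, thorax, abdomen and pelvis will be performed at visit 9 (week 25"). The flowchart agrees: the row "Disease / response assessment (clinical/imaging") is marked at visit 1, visit 4, EOT and follow-up. The row "Physical examination, incl. tumour size (lymph nodes, spleen, liver") is marked at visit 7 as well, and safety laboratory samples are taken there. On EOT timing, footnote 12 says: "If 12 infusions has been administered the EOT should be performed at the latest in week 26 (day 77±5 of course 3").

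Under SAP section 5.2.2, a patient with no progression, death or new lymphoma therapy is "censored at the date of the last response assessment during which the patient was evaluable and did not have the event". Imaging and physical assessment both qualify, but an assessment is evaluable only when CR, CRu, PR, SD or PD was assigned.

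**The concern.** A site cannot satisfy section 3.2 and also follow the course 3 flowchart and section 6.2.2.3 as written. The flowchart row and the text of 6.2.2.3 agree with each other, so the gap does not come from a broken table.

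The conflict matters for PFS and FFS. At visit 7 the nodes, spleen and liver are examined, but the schedule asks for no response category. Under the SAP's definition that examination cannot move the censoring date. Whether it could date a later progression is not stated. The earliest-date rule in SAP section 5.2.2 covers examinations that contribute to one disease assessment over several days, and visit 7 falls 34 days before EOT.

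Protocol section 3.1 admits to course 3 only patients with response, or stable disease with clinical benefit. The longest scheduled interval between recorded assessments therefore falls on patients who contribute to the later part of the Kaplan-Meier curves.

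**Working it through.** **Inputs**

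- Last course 3 infusion and visit 4 assessment: day 22 (course 3 flowchart).
- Visit 7: day 43; physical examination with tumour size, no response entry (course 3 flowchart).
- CT at visit 9: day 71 ±5 (course 3 flowchart; 6.2.2.3).
- EOT after 12 infusions: day 77 ±5 (footnote 12).
- Observation after the last course 3 infusion: 55 days (3.1).
- Follow-up disease evaluation: at least every 6 weeks, so at most 42 days apart (3.2).

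**The plan's own figure.** Day 77 − day 22 = 55 days, which matches the 55 days in section 3.1. With the ±5 window the range is 50 to 60.

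**Where the section 3.2 assessment falls.** Day 22 + 21 = day 43, which is visit 7.

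**Scheduled intervals after day 22**

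- To EOT: 55 days (50 to 60).
- To the day 71 CT: 71 − 22 = 49 days (44 to 54). This applies if the earliest-date rule carries an EOT finding back to the CT that supports it.
- With a day 43 entry: 21 + 34 days (EOT-dated) or 21 + 28 days (CT-dated).

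**Comparators.** Within courses 1 and 2, assessments fall on days 1, 22 and 43, so planned spacing is 21 days. From day 43 to day 1 of the next 49-day course is 7 days. Against follow-up, the excess is 55 − 42 = 13 days or 49 − 42 = 7 days.

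**Mean dating delay (illustrative).** Assume that progression is uniform over the whole interval and is found only at scheduled assessments. For gaps g₁, g₂, … the mean delay is Σg² / (2Σg).

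- EOT-dated, as scheduled: 55² / (2 × 55) = 27.5 days.
- EOT-dated, with day 43: (21² + 34²) / (2 × 55) = (441 + 1156) / 110 = 14.5 days.
- CT-dated, as scheduled: 49² / (2 × 49) = 24.5 days.
- CT-dated, with day 43: (21² + 28²) / (2 × 49) = (441 + 784) / 98 = 12.5 days.

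The reduction is 13.0 or 12.0 days. By the SAP's conversion (days × 12 / 365.25) that is 0.43 or 0.39 month.

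**Censoring.** A progression-free patient examined on day 43 and then lost with no EOT visit is censored at day 22. That forgoes 43 − 22 = 21 days of follow-up.

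**The case against.** The other side has several sound points.

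- **The visit itself is not missing.** Section 3.2 asks for an examination, a clinical assessment of the lymphoma and blood samples; it does not mention a response category. The tumour-size examination and the bloods are scheduled at visit 7. A reader might infer that course 3 drops the three-week check altogether. The flowchart does not support that: only the disease/response entry is absent.
- **Late dating is possible, not certain.** Course 3 has visits on days 29, 36, 43, 57 and 71. The SAP accepts progression captured by the investigator with or without imaging, and section 6.2.3.1 requires the date on which progression was first documented. The delay figures ignore progression found between scheduled assessments.
- **Leaving early does not usually send censoring back to day 22.** Sections 3.3.4.1 and 6.2.3.1 call for a prompt EOT visit, with efficacy assessed, when a patient stops. Only patients lost without that visit are affected, and the documents give no number for them.
- **Benefit-dependent bias is a tempting reading, but weakly supported.** Patients who stop earlier without progression move to follow-up at intervals of up to 42 days, so the contrast with them is 7 to 13 days. Section 6.1 also allows an infusion to be postponed by up to 3 weeks, so 21 days in courses 1 and 2 is the planned spacing only. There is no control arm and no formal test.
- **Section 3.2 could be changed instead.** It is the one place that disagrees with the other two, and amending it would also remove the contradiction.

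All of this limits the consequence. It does not reconcile the sections, and it does not give the visit 7 examination a response category that the SAP can use.

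**Conclusion.** The contradiction is real: section 3.2 applies the three-week assessment to every course, while the course 3 flowchart and section 6.2.2.3 have no disease/response assessment at visit 7. As scheduled, 49 or 55 days pass after day 22 before the next datable assessment, depending on whether the earliest-date rule applies. The likely effect is coarser dating of progression, about 12 to 13 days on average, under the assumptions of uniform progression and detection only at scheduled assessments.

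The effect is confined to PFS and FFS in patients who reach course 3. These are secondary endpoints analysed descriptively. The MTD rests on DLTs up to 7 days after the second administration and is untouched. The documents do not support a claim that PFS and FFS are materially biased, or that progression in course 3 will be dated late in every case.

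**What to change.** Reconcile section 3.2 with the course 3 flowchart and section 6.2.2.3 by adding a clinical disease/response assessment at course 3 visit 7 (day 43), with the category recorded from the examination already scheduled there. No extra imaging is needed: footnote 3 of the course 3 flowchart already lets the assessment rest on clinical judgement when there is no recent CT. Amending section 3.2 alone would remove the contradiction but leave the 49- or 55-day interval.

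The cost is one flowchart mark, one sentence in 6.2.2.3 and one more eCRF entry at an existing visit. The downside is that course 3 patients already treated will not have the entry. Section 7.6 counts 41 patients enrolled and up to 12 to come, so assessment spacing will differ slightly between earlier and later cohorts. The report should say so.
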